4.0 STAGING CRITERIA

PRIMARY TUMOR (T) (AJCC Seventh Edition, 2009)

Ta	Non-invasive papillary carcinoma
CIS	Carcinoma in situ : "flat tumor"
T1	Tumor invades subepithelial connective tissue

HISTOLOGIC GRADE (G)

WHO 2004/ISUP

Low-grade
High-grade

5.0 ELIGIBILITY CRITERIA

Each of the criteria in the following section must be met in order for a patient to be considered eligible for registration. Use the spaces provided to confirm a patient's eligibility. For each criterion requiring test results and dates, please record this information on the Onstudy Form and submit via Medidata Rave® (see [Section 14.0](#)). Any potential eligibility issues should be addressed to the SWOG Statistics and Data Management Center in Seattle at [name] or [contact] prior to registration.

In calculating days of tests and measurements, the day a test or measurement is done is considered Day 0. Therefore, if a test is done on a Monday, the Monday 3 weeks later would be considered Day 21. This allows for efficient patient scheduling without exceeding the guidelines. If Day 21 or 42 falls on a weekend or holiday, the limit may be extended to the next working day.

5.1 Study Chair Approval Requirement

Patients' disease related criteria ([Section 5.2](#)) and BCG-unresponsiveness ([Section 5.3a](#)) must be discussed with at least one of the **S1605** Study Chairs prior to registration. The **S1605** Pre-Registration Study Chair Approval form must be signed by one of the **S1605** Study Chairs to indicate approval within 30 days prior to registration.

The **S1605** Pre-Registration Study Chair Approval Form is located in [Section 18.4](#). See [Section 14.4a](#) for form submission requirements.

5.2 Disease Related Criteria

- a. Patients must have histologically proven, recurrent, non-muscle invasive urothelial carcinoma of the bladder within 60 days prior to registration. The carcinoma must be Stage T1 High-Grade, Stage CIS, or Stage Ta High-Grade (see [Section 5.2f](#) for high-grade T1).
- b. Patients with mixed urothelial carcinoma and a glandular and/or squamous component will be eligible for the trial, but the presence of other histologic variants, pure adenocarcinoma, or pure squamous cell carcinoma, or pure squamous carcinoma in situ will make a patient ineligible.
- c. Patients must have had all visible tumor resected completely within 60 days prior to registration. CIS disease is not expected to be completely excised. All patients must have tumor tissue from the histologic diagnosis of recurrence (see [Section 5.2.a](#)) available for central pathology review submission (see [Section 12.0](#)). Failure to submit these materials will make the patient ineligible for this study.
- d. Patients must have had cystoscopy confirming no visible papillary tumor within 21 days prior to registration. (CIS disease is not expected to have been completely excised). If the TURBT or bladder biopsy falls within 21 days of registration it will fulfill this criterion.
- e. Patients must have had urine cytology within 21 days prior to registration. Cytology for patients with CIS component is not expected to be negative for malignant cells. If the cytology for male patients with only Ta/T1 disease in the absence of CIS is positive for malignant cells, patient must have had a biopsy of the prostatic urethra within the previous six months.
- f. All patients with T1 urothelial carcinoma at study entry must undergo re-TURBT within 60 days prior to registration, and must have evidence of uninvolved muscularis propria in the pathologic specimen from either the first or the second TURBT. Tissue from the re-resection must be submitted for central review in addition to the tissue from the first TURBT (see [Section 12.0](#)). The TURBT that identified the recurrent T1 disease may have taken place more than 60 days prior to registration but not more than 120 days. Patients with high grade Ta or CIS do not require a re-TURBT, but if this is performed at the discretion of the treating physician, the second TURBT must be within 60 days of registration. There is no requirement for muscularis propria in the specimen of Ta/CIS patients, but the tissue from the first and second TURBTs must be submitted for central review. If a patient with Ta/T1 disease undergoes repeat TURBT, the patient will be stratified as having CIS if there is CIS on either TURBT.
- g. Patients must not have had urothelial carcinoma in the prostatic urethra within the previous 24 months or muscle invasive urothelial carcinoma of the bladder at any time. Patients with prior urothelial carcinoma in the upper urinary tract within the previous 24 months will only be eligible if they had \leq T1 carcinoma and were treated with nephroureterectomy. Patients must have a CT or MRI (including CT-

IVP, CT-urogram or MR-urogram) of the abdomen and pelvis to rule out upper tract malignancy and intra-abdominal metastases within 90 days prior to registration. If a patient cannot tolerate intravenous contrast, a retrograde pyelogram should be performed within 90 days prior to registration.

- h. Patients must be deemed unfit for radical cystectomy by the treating physician, or the patient must refuse radical cystectomy, which is considered standard of care for these patients. The reason for patients not to undergo cystectomy will be clearly documented.

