- Ψ For all patients with CIS at study entry, one urine cytology slide is required for central pathology review. See [Section 12.0](#) for instructions.
- Θ Baseline histology used to diagnose disease for eligibility (from biopsy or TURBT), per [Section 5.1a](#).
- λ Baseline labs (except TSH) to be obtained within a window of 3 weeks.

Allowable windows

Treatment must begin within 7 calendar days of registration.

Allowable windows for scheduled disease assessments performed every 12 weeks is +/- 14 days, every 24 weeks is +/- 14 days. The window is to be calculated from the scheduled date of the procedure/assessment.

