11.0 STATISTICAL CONSIDERATIONS

11.1 Patient Populations

Eligible patients are defined as registered patients who met all the pre-registration eligibility criteria listed in Section 5 that were in effect at the time of the 12/14/18 amendment. The determination of eligibility regarding Disease Related Criteria will be based on local pathology review.

Evaluable patients are defined as registered patients who received any amount of study drug (atezolizumab).

Efficacy analyses will be based on patients who are determined to be both eligible and evaluable as defined above.

Safety analyses will be based on patients who are determined to be evaluable as defined above. Patients who are registered in the study but who do not receive any study drug will not be included in safety analyses.

11.2 Estimate of Sample Size:

A sample size of 135 eligible patients (evaluable) will be enrolled over 36 months with 18 months of additional follow-up. Our goal is to enroll 70 patients with a CIS component and 65 patients with Ta or T1 disease only. One stratum may be closed prior to accrual completion to ensure adequate patient numbers in both disease groups. An additional 50% will be enrolled to account for ineligibility or initial treatment refusal resulting in a total sample size of 202. With Revision #5 (Version Date 12/14/18) a pre-registration Study Chair approval form was enacted which has significantly reduced the rate of ineligible registrations.

11.3 Analysis:

There will be two co-primary aims for this study: The first objective to be tested involves the complete response rate in the subset of patients with CIS (see [Section 10.1](#)). The second co-primary objective involves event-free survival at 18 months for all evaluable patients. A hierarchical approach will be used to test the two co-primary aims. The CIS aim will be tested first. Only if the result is statistically significant will the second primary objective be evaluated. Only patients who received at least one dose of atezolizumab per protocol will be evaluable for these two primary objectives. Both co-primary tests will be conducted at the one-sided 0.05 significance level.

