12.0 DISCIPLINE REVIEW

12.1 Central Pathology Review

- a. All patients registered on this study will undergo central pathology review to confirm diagnosis and determine eligibility. Pathology material must be available for this purpose (see [Section 5.0](#)). The review will verify the histologic diagnosis of non-muscle invasive urothelial carcinoma of the bladder and determine the grade and pathologic stage of the tumor. Pathologic review will be conducted on an ongoing basis, but will not be verified prior to patient registration and initiation of study treatment. Similarly, all patients with CIS will undergo central review of urine cytology at 13 and 25 weeks in order to verify complete response. All bladder biopsies taken to evaluate a suspicious lesion in any patient or at the mandatory 25 week time point in patients with CIS will be reviewed centrally, but decisions to continue study treatment will be based on the local pathologist's interpretation.
- b. All pathology submissions must be entered and tracked using the SWOG online Specimen Tracking system. See [Section 15.1b](#) for information about this system.
- c. Pathology materials are to be submitted to the SWOG Biospecimen Bank (Lab #201). The Bank will scan the slides and send to the study pathologist, [REDACTED], M.D.

All specimens must be shipped at room temperature for overnight delivery, Monday through Thursday (no weekend or holiday deliveries accepted).

- d. The following materials are to be submitted for review:

Tissue

1. Three (3) representative diagnostic tumor H & E stained slides.
2. One copy of corresponding surgical pathology report.

Urine Cytology (only patients with CIS component at study entry)

1. 1 urine cytology slide (This should be the routine slide used by the site to do the cytology.)
2. Cytology report

The tissue and cytology specimens used by the study site for diagnosis must be submitted. No special specimen preparation is required. A copy of the Shipment Packing List produced by the Specimen Tracking system must be printed and placed in the pocket of the specimen bag if it has one, or in a separate resealable bag.

- e. Specimens and corresponding reports must be submitted at the following time points:

Tissue

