1. Baseline collection, submitted within 7 days after registration. All tissue obtained within 60 days prior to registration for histologic confirmation of recurrent disease (see [Section 5.1](#)). For T1 patients, tissue from the prestudy re-resection and original TURBT (even if > 60 days prior to registration) must be submitted.
2. All subsequent biopsies for suspected recurrence including negative biopsies and those that show any recurrence (high or low grade).
3. FOR PATIENTS WITH CIS DISEASE AT STUDY ENTRY: Within 28 days after Week 25 biopsy.

Urine Cytology

1. FOR PATIENTS WITH CIS DISEASE AT STUDY ENTRY: Within 28 days after Week 13 and Week 25 disease assessments.

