14.0 DATA SUBMISSION SCHEDULE

14.1 Data Submission Requirement

Data must be submitted according to the protocol requirements for **ALL** patients registered, whether or not assigned treatment is administered, including patients deemed to be ineligible. Patients for whom documentation is inadequate to determine eligibility will generally be deemed ineligible.

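### Sections 5.2c, 14.1 and 11.1, read together, let a treated patient drop out of both co-primary analyses because tissue or documents were not submitted after registration, and no all-treated efficacy analysis is planned to show the effect.

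*Combined protocol and SAP*

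**What the plan says.** **Tissue.** Section 5.2c requires tissue from the qualifying recurrence to be available for central review and adds: "Failure to submit these materials will make the patient ineligible for this study". Section 12.1e sets the timing: "Baseline collection, submitted within 7 days after registration". The allowable windows in Section 9.1 say: "Treatment must begin within 7 calendar days of registration". Section 12.1a states that central review serves to confirm diagnosis and determine eligibility, but that it "will not be verified prior to patient registration and initiation of study treatment".

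**Documents.** Section 14.1 says: "Patients for whom documentation is inadequate to determine eligibility will generally be deemed ineligible". It also requires full data on every registered patient, including those found ineligible.

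**Analysis sets.** Section 11.1: "Eligible patients are defined as registered patients who met all the pre-registration eligibility criteria listed in Section 5" (those in effect at the 12/14/18 amendment). It continues: "The determination of eligibility regarding Disease Related Criteria will be based on local pathology review". Evaluable means having received any atezolizumab. Then: "Efficacy analyses will be based on patients who are determined to be both eligible and evaluable as defined above". Safety uses all treated patients. Section 11.3, by contrast, describes the EFS co-primary objective as applying to all evaluable patients, without mentioning eligibility.

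**Allowance.** Section 11.2 plans 135 eligible and evaluable patients (70 with CIS, 65 with Ta/T1 only). It adds 50%, to 202, for ineligibility or initial treatment refusal. It notes that the Study Chair approval form has significantly reduced ineligible registrations.

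**The concern.** Both primary decisions in this single-arm trial compare an absolute rate with a fixed benchmark, so the rule for who is in the denominator matters directly. Section 5.2c attaches ineligibility to something the site does, or fails to do, after registration and possibly after dosing. That is not a baseline characteristic of the patient. Under 11.1, such a patient stays in the safety set but leaves CR and EFS.

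The exclusion also seems to serve no purpose for the efficacy set. Section 11.1 decides disease eligibility on local pathology, and the central slides serve the agreement objective in Section 1.3a.

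Missing material is handled in opposite ways. A CIS patient with no Week 25 biopsy counts as a non-responder (11.3), which is conservative. A CIS patient whose baseline slides never arrive is removed from the denominator, which is neutral only if such patients respond like the rest.

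Because EFS is tested only if CR succeeds, a change in the CR denominator also affects whether EFS is tested at all.

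**Working it through.** **1. The route to exclusion.**
- Day 0: registration. Slides and first dose are both due by Day 7 (12.1e, 9.1), in no fixed order.
- Slides not sent: ineligible (5.2c). Documents inadequate to judge eligibility: generally ineligible (14.1).
- Ineligible but treated: outside the efficacy set, inside the safety set (11.1).
- Sections 11.1 and 14.1 give no cut-off date for the ruling and do not say that it is made without knowledge of outcome.

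**2. The plan's own figures.**
- Registrations: 135 × 1.5 = 202.5, stated as 202. Reproduced.
- Allowance: 202 − 135 = 67, and 67/202 = 33.2%. The documents do not split the 67 between refusal before treatment, ineligibility on clinical grounds, and missing slides or documents.
- CR rule, at least 28 of 70, null 30%, alternative 50%: the single-stage exact binomial gives P(X ≥ 28 | 70, 0.30) = 0.0476 and P(X ≥ 28 | 70, 0.50) = 0.964. With the interim stop for fewer than 7 CRs in the first 25 patients, these become 0.0464 and 0.960, matching the stated 4.6% and 96%.

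**3. Fragility of a result that just passes.** Suppose 28 of 70 eligible CIS patients respond, and k further treated CIS patients were excluded and did not respond. The exact one-sided p-value is P(X ≥ 28 | 70 + k, 0.30), single-stage:

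| k | CR in all treated | p |
|---|---|---|
| 0 | 28/70 = 40.0% | 0.048 |
| 1 | 28/71 = 39.4% | 0.057 |
| 5 | 28/75 = 37.3% | 0.105 |
| 10 | 28/80 = 35.0% | 0.195 |

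If the single added patient had responded instead, 29/71 = 40.8% and p = 0.034. The result can move either way.

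**4. Effect on the error rate, under assumed values.** Let the true CR in all treated CIS patients be 30%, the excluded fraction f, and the CR among the excluded q. The rate in the analysed set is (0.30 − f·q)/(1 − f), and the chance of declaring success is P(X ≥ 28) with n = 70 at that rate. Neither f nor q is in the documents.

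| f | q | Rate in analysed set | P(success) |
|---|---|---|---|
| any | 30% | 30.0% | 0.048 |
| 5% | 15% | (0.30 − 0.0075)/0.95 = 30.8% | 0.064 |
| 10% | 15% | (0.30 − 0.015)/0.90 = 31.7% | 0.087 |
| 20% | 15% | (0.30 − 0.03)/0.80 = 33.8% | 0.163 |
| 10% | 45% | (0.30 − 0.045)/0.90 = 28.3% | 0.024 |

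Exclusion unrelated to response leaves the error rate alone. Losing poorer responders inflates it, and losing better responders deflates it.

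**The case against.** **The analysis-set definition may already neutralise the clause.** Section 11.1 speaks of pre-registration criteria and local pathology. What 5.2c requires before registration is that tissue be available; sending it is a later act. This reading is reasonable and may be what was intended. But the sentence on non-submission sits inside a Section 5 criterion, 12.1a still gives central review the task of determining eligibility, and nothing cancels either. The wording in force at the 12/14/18 amendment is not reproduced separately, so it cannot be checked.

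**There is little outcome to react to.** Slides and baseline reports are due within 7 days of registration (12.1e, 14.4a). The first scheduled disease assessment is at Week 13, and CR is judged at Week 25. This stands: a reader might infer that early failures are selectively removed, but the documents do not show it. They leave open when the final ruling is made and whether outcomes are then known.

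**Section 14.1 is limited.** It concerns documents needed to judge eligibility and says only that exclusion generally follows. This stands too; not every missing form disqualifies a patient.

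**The one-third figure does not measure this problem.** A reader might infer that up to a third of registrations could be lost through paperwork, or might load the whole CIS allowance (70 × 0.5 = 35) onto treated patients with poor response and bring the all-treated CR down to the null. The documents do not support either. The allowance includes all clinical ineligibility and people who never started treatment, the Study Chair form has reduced ineligible registrations, and no response rate among excluded patients is given. Some of them, such as patients who turn out not to be BCG-unresponsive, could do better than the rest.

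**Early failures are kept elsewhere.** Death is an EFS event and a missing Week 25 biopsy counts as non-response. Both rules apply only to patients already in the efficacy set.

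**Conclusion.** The point holds as an inconsistency with a possible effect on both co-primary results. It is not a demonstrated bias. The text allows a treated patient to be removed from CR and EFS for a submission failure after registration, while 11.1 and 11.3 contain wording that points the other way. No efficacy analysis in all treated patients is clearly specified. The 11.3 phrase for EFS would amount to one under 11.1's own definition of evaluable, but it conflicts with 11.1's efficacy rule, and nothing comparable is set out for CR.

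The number of patients affected and the direction of any effect are unknown. What can be said is that at the passing threshold one excluded, treated non-responder is enough to move the exact p-value from 0.048 to 0.057, and five move it to 0.105. This assumes a result of exactly 28/70 and non-response in every added patient. At the design alternative of 50% (35/70) there would be far more room.

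**What to change.** 1. Reconcile 5.2c, 12.1a, 14.1, 11.1 and 11.3. State that failure to submit central slides is a protocol deviation, and missing data for objective 1.3a, but does not remove a patient from the efficacy set. Because 11.1 ties eligibility to the criteria in effect at the 12/14/18 amendment, this must be written into 11.1 itself; editing 5.2c alone would not reclassify anyone.
2. State that eligibility is judged only on facts that existed before registration, by people who do not refer to outcome. For patients already assessed, document how and when the ruling was made.
3. Keep the eligible-and-evaluable set as primary for both co-primary tests, and make the EFS population in 11.3 agree with 11.1.
4. Prespecify CR and 18-month EFS in all treated patients as a sensitivity analysis, and tabulate each exclusion with its reason, separating clinical ineligibility, missing slides or documents, and no treatment.

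The cost is an amendment to the analysis wording and some extra analysis. No new patients or procedures are needed, since 14.1 already requires the data. The all-treated figure may be less favourable than the primary one.

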5.3 Prior/Concurrent Therapy Criteria

- a. Patients must be BCG-unresponsive. A patient is BCG-unresponsive if they meet one or more of the following criteria:

- Patient has persistent or recurrent high-grade Ta/CIS urothelial carcinoma after completing therapy with at least induction BCG (≥ 5 doses) and first round maintenance (≥ 2 doses) or second induction BCG (≥ 2 doses). Both rounds of BCG must have been administered within a 12 month period. These patients must have either had high-grade Ta tumors and did not achieve a disease-free state for more than 6 months following last dose of BCG, or they had CIS and did not achieve a CR. **S1605** registration must occur within 9 months of the last dose of BCG.
 - If a patient does not meet these criteria only because the last dose of BCG was more than 9 months ago, the patient may become eligible if he/she shows histologically proven high-grade recurrence after an additional round of induction or maintenance BCG (≥ 3 doses) within 9 months prior to registration.
- Patient has persistent or recurrent high grade T1 urothelial carcinoma after completing therapy with at least induction BCG (≥ 5 doses). Patients with recurrent high grade T1 urothelial carcinoma after additional rounds of BCG will also be eligible, but one round of maintenance therapy or a second induction is not a pre-requisite for these patients. Trial registration must occur within 9 months of the last dose of BCG.
 - If a patient does not meet these criteria only because the last dose of BCG was more than 9 months ago, the patient may become eligible if he/she shows histologically proven high grade recurrence after an additional round of induction or maintenance BCG (≥ 3 doses) within 9 months prior to registration.
- Patient achieves disease-free state at 6 month time point (i.e., complete response; presence of only low-grade tumor at this timepoint is still considered complete response) after induction and maintenance (or second round of induction) BCG but later experiences a high-grade Ta/T1 recurrence (with or without concomitant CIS) within 6 months after the last dose of BCG or recurrent CIS (in absence of concomitant Ta/T1 tumor) within 12 months after the last BCG dose. The time of eligibility is measured from the last dose of BCG to the time of disease recurrence. The patient must be registered on the trial within 60 days of this recurrence, or within 60 days of a re-TURBT if indicated. See [Section 5.2f](#) for TURBT requirements.

- b. All adverse events associated with any prior surgery and intravesical therapy must have resolved to Grade ≤ 2 prior to registration.

- c. Patients must not have had prior systemic chemotherapy for bladder cancer or systemic immunotherapy, including, but not limited to interferon alfa-2b, high dose IL-2, PEG-IFN, anti-PD-1, anti-PD-L1, intra-tumoral. Patients must not have had vaccine therapies within 6 weeks prior to registration. Patients must not have received or be planning to receive any of the prohibited therapies listed in [Section 7.3](#) during protocol treatment. Prior intravesical administration of chemotherapy, interferon, Vicinium™ (VB4-845), BC-819 or Instiladrin™ (rAd-interferon-alpha/Syn3) is allowed if all other criteria are met and the last administration was ≥ 30 days before registration.
- d. Patients must not be planning to receive concomitant other biologic therapy, radiation therapy, intravesical chemotherapy, surgery, or other anti-cancer therapy while on this protocol.
- e. Patients must not have received any prior radiation to the bladder for bladder cancer.
- f. Patients must not have received treatment with systemic immunosuppressive medications (including, but not limited to, prednisone, cyclophosphamide, azathioprine, methotrexate, thalidomide, and anti-tumor necrosis factor [anti-TNF] agents) within 4 weeks prior to registration. Exceptions: (1) Patients may have received acute, low dose, systemic immunosuppressant medications (e.g., a one-time dose of dexamethasone for nausea); (2) The use of inhaled corticosteroids and mineralocorticoids (e.g., fludrocortisone) for patients with orthostatic hypotension or adrenocortical insufficiency is allowed.
- g. Patients must not have received a live, attenuated vaccine within 4 weeks before registration or anticipation that such a live, attenuated vaccine will be required during the study and up to 5 months after the last dose of atezolizumab.
- Influenza vaccination should be given during influenza season only (approximately October to March). Patients must not receive live, attenuated influenza vaccine within 4 weeks prior to Cycle 1, Day 1 or at any time during the study.
- h. Patients must not require treatment with a RANKL inhibitor (e.g. denosumab) who cannot discontinue it before treatment with atezolizumab.

